### 1 INTRODUCTION

HeartMate 3 (HM3) Left Ventricular Assist System (LVAS) is a centrifugal, fully magnetically levitated, continuous-flow pump designed to facilitate hemocompatibility by reducing shear stress on blood elements and to optimize pump washout by intrinsic pulsatility.

The Multicenter Study of MagLev Technology in Patients Undergoing Mechanical Circulatory Support Therapy with HeartMate 3 (MOMENTUM 3) trial 2-year data demonstrated an absence of confirmed pump thrombosis requiring pump exchange and marked reduction in stroke rates. On the backdrop of conventional anticoagulation protocols used in the study, observed bleeding complication rates in HM 3 were reduced, yet there is a need for further improvement as the overall intensity of conventional anti-thrombotic therapy represents a major contributor to non-surgical bleeding-related outcomes.

The HM3 LVAS Instructions for Use (IFU) recommend maintaining patients on Warfarin and Aspirin for long-term anticoagulation therapy. Recent results of The Minimal AnticoaGulation EvaluatioN To aUgment heMocompatibility (MAGENTUM 1) pilot study has demonstrated substantially lower-intensity anticoagulation (INR range 1.5 - 1.9) is achievable and supports the safety of lower targets with select patients implanted with the HeartMate 3 beyond 1 year with no thromboembolic complications or pump thrombosis. The observed outcomes were similar to those with the higher intensity anticoagulation targets and further support a signal of enhanced intrinsic thromboresistance of the HM3.

Direct oral anticoagulants (DOACs) are a class of drugs which directly exert therapeutic effect on specific coagulation factors. Broadly, they can be categorized as direct thrombin inhibitors (dabigatran) and factor Xa inhibitors (apixaban, rivaroxaban, and edoxaban) or FXai. Warfarin, which inhibits vitamin K dependent synthesis of coagulation factors in a manner that prevents activation of these factors, has wide inter-individual variation in metabolism and a narrow therapeutic window, as well as both food-drug and drug-drug interactions; the result is that patients taking warfarin require frequent monitoring of the anticoagulant effect to maintain safety and efficacy. The DOAC directly enter the blood to bind to the activated coagulation factor target; they have predictable pharmacokinetics, little interindividual variation in metabolism, few drug-drug interactions, and no interactions with foods. The large phase 3 RCT in both AF and VTE established both efficacy and safety—without the need for monitoring. The FXai may provide better anticoagulation than the oral direct thrombin inhibitor due to their action earlier in the coagulation cascade prior to the generation of

thrombin which may ameliorate the likelihood of initiation of the feedback loop resulting in >1000-fold increase in thrombin production. Of the studied FXai, apixaban has the lowest major bleeding complication rate and has not been shown to increase GI-bleeding. It also has the least dependence on renal clearance. Consequently, with the documented enhanced hemocompatibility of the HeartMate 3 and the potential for reduced major bleeding with apixaban in indicated patient populations, we provide the rationale that patients with the HM3 are in clinical equipoise to be randomized in a feasibility study of a new antithrombotic strategy testing apixaban with or without aspirin compared to the current standard of care warfarin and aspirin in a rigorously structured study to evaluate safety in stable patients with the HM3 device.

#### **Apixaban Safety and Efficacy Data**

Apixaban is a DOAC that directly inhibits Factor Xa (FXai) in the coagulation cascade. Its therapeutic effect is more consistent and predictable due to its mechanism of action, and it is not subject to the disadvantages inherent to Vitamin K antagonist (VKA) anticoagulants. In phase 3 clinical trial that resulted in FDA approval, involving 18,201 patients with non-valvular AF, Apixaban was shown to be non-inferior in antithrombotic effect and superior in terms of major bleeding relative to VKA anticoagulants (ARISTOTLE study; NCT00412984). Major bleeding, per the International Society on Thrombosis and Haemostasis (ISTH) definition, was reduced with Apixaban relative to VKA, primarily due to a 58% reduction in intracranial hemorrhage (ICH) and 21% drop in locations other than the gastrointestinal (GI) tract. Clinically relevant non-major bleeds were also significantly reduced in this study. GI bleeding was not significantly different between Apixaban and warfarin.

In the AMPLIFY study (NCT00643201), the safety and efficacy of apixaban for the prevention of recurrent venous thromboembolic (VTE) events and death due to VTE were compared with warfarin in 5,395 patients with acute VTE. Apixaban was found to be non-inferior to warfarin preventing recurrent VTE events (RR: 0.84; 95% CI: 0.6 – 1.18 ), and major bleeding was reduced by 69% in the apixaban group. In a meta-analysis of DOAC studies in the VTE population, FXa inhibitors were found to have 60 % lower rate of ICH and fatal bleeds compared to VKA. In a retrospective study of Medicare beneficiaries, 36% fewer patients were hospitalized for upper-GI bleeding with apixaban than with warfarin. In another post-market study, apixaban was compared with rivaroxaban and dabigatran using propensity-matched cohorts of Medicare beneficiaries, with non-valvular AF, in terms of safety and efficacy. Apixaban was found to have a lower risk of causing GI and major bleeds than the other DOACs. No differences were seen between the three DOACs in strokes or systemic embolism. Even in cancer patients in whom the risk of bleeding is higher than in other populations, treatment of VTE with apixaban showed no increase in major bleeding compared to dalteparin, unlike edoxaban and rivaroxaban, both of which had increased major bleeding compared to dalteparin.

#### The rationale for Apixaban use with the HeartMate 3

There have been no studies to date that have systematically evaluated the feasibility of using apixaban alone or combined with low dose aspirin in HM3 patients. All the primary phase 3 clinical trials assessing DOACs have focused on patients with non-valvular atrial fibrillation or venous thromboembolism with or without cancer.  Within the literature, there are sparse reports of apixaban use with LVAD patients due to recurrent bleeding or non-compliance with warfarin. These small sample size studies reported encouraging low rates of thromboembolic events. In all but one instance, aspirin was withheld due to the history of bleeding events. Patients in these studies either had the HeartMate II or HeartWare HVAD.

Reduction in bleeding and thromboembolic events with HeartMate 3 compared to the HeartMate II was demonstrated by the MOMENTUM 3 IDE Trial. Yet, bleeding complications remain a burdensome limitation while on support and represent a significant cause of rehospitalizations and morbidity. Independently, both a reduction in major bleeding events and stable anticoagulation intensity constitute a compelling potential benefit of a modified antithrombotic strategy with a direct oral anticoagulant. However, these apixaban associated benefits remain to be validated in advanced heart failure population supported with the HeartMate 3 LVAS. Therefore, the objective of this study is to assess safety and feasibility of apixaban use in HM3 supported patients.

### 2 STUDY OBJECTIVES

#### 2.1 PRIMARY ENDPOINT

The primary endpoint to evaluate the safety and feasibility of apixaban with the HeartMate 3 LVAS is survival free of major HRAEs (hemocompatibility related adverse events) at 90 days post-enrollment. The primary analysis will compare the apixaban groups (n=30) to control (n=15). A separate analysis will compare the primary endpoint in patients randomized to receive aspirin (n=15) and no-aspirin (n=15) within the apixaban group.

Major HRAEs include:

- Stroke (ischemic/hemorrhagic)
- Pump thrombosis
- Severe bleeding (see Appendix II)
- Peripheral arterial thromboembolic events

HRAEs are influenced by several patient-specific risk factors, including anticoagulation, poor general health, altered circulation, the pump's hemocompatibility, and the presence of other comorbidities (e.g., AF, infections, etc.). In standard use, clinicians balance the risk of stroke and other thromboembolic (TE) events with the increased risk of bleeding when prescribing

anticoagulation or antiplatelet medications. Therefore, a composite endpoint comprising TE, bleeding, and pump-related events were chosen for the analysis.

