#### **2.2 SECONDARY ENDPOINTS**

The secondary endpoints include an evaluation of the following adverse events per INTERMACS definitions (version 5.0) throughout the study period:

- Stroke (ischemic/hemorrhagic)
- Pump thrombosis
- Major bleeding
- GI Bleeding
- Peripheral arterial thromboembolic events
- Transient ischemic attack
- Hemolysis
- Venous thromboembolism
- Myocardial infarction
- Right heart failure
- Cardiac arrhythmias
- Liver and kidney dysfunction
- Death due to any cause

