### 3 STUDY DESIGN

A prospective, single-center, randomized controlled trial of the feasibility and safety of apixaban in HeartMate 3 patients.

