#### 5.2.6 Changes to the antithrombotic regimen

Any changes to the designated antithrombotic regimen based on randomization algorithm will be documented during the follow-up visits or with the occurrence of an adverse event.

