## DOT HM3 Study – Statistical analysis plan

Stable HM3 patients who have not suffered a Major hemocompatibility-related adverse after index hospitalization discharge and are at least 3 months post-implant will be screened for participation in the study. Upon meeting the study criteria and patient informed consent, the individuals will be randomized to either continued therapy with a Vitamin K antagonist and aspirin or conversion to apixaban 5 mg twice a day in a 1:2 manner; the apixaban group will be stratified further by 1:1 randomization to continued use of 100 mg aspirin once daily or cessation. Thus, 45 patients are planned to be enrolled and randomized in 3 subgroups of 15 patients in each arm. The sample size of 45 patients was calculated to be sufficient to elucidate any safety signal. After 180 days follow-up is reached, the Vitamin K antagonist and aspirin arm will be transitioned to apixaban and randomized in a 1:1 manner to groups with or without aspirin.

Survival free of a hemocompatibility-related adverse events event (Stroke ischemic/hemorrhagic, Pump thrombosis, Severe bleeding, Peripheral arterial thromboembolic events) at the endpoint of 90 days will be evaluated as primary endpoint as proportion of success calculated between the apixaban and the warfarin arms. The prevalence (percent of patients with events) and incidence (event rates in events per pt-year) of adverse events and rehospitalizations will be determined. The secondary endpoints include an evaluation of the following adverse events per INTERMACS definitions (version 5.0) throughout the study period:

- Stroke (ischemic/hemorrhagic)
- Pump thrombosis
- · Major bleeding
- GI Bleeding
- Peripheral arterial thromboembolic events
- Transient ischemic attack
- Hemolysis
- Venous thromboembolism
- Myocardial infarction
- Right heart failure
- Cardiac arrhythmias
- Liver and kidney dysfunction
- Death due to any cause

Time to event analyses will be done by Kaplan-Meier analysis. The overall outcomes being evaluated for clinical safety as assessed by the study's oversight committee.

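### Feasibility is a stated aim, but the only endpoint assigned to it does not depend on whether patients stay on apixaban

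*Protocol*

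**What the plan says.** Feasibility is a named aim in three places in the Protocol. The rationale in section 1 says that "the objective of this study is to assess safety and feasibility of apixaban use in HM3 supported patients". Section 3 describes a "randomized controlled trial of the feasibility and safety of apixaban in HeartMate 3 patients". Section 2.1 gives both aims one measure: the primary endpoint "to evaluate the safety and feasibility of apixaban with the HeartMate 3 LVAS is survival free of major HRAEs", assessed at 90 days. The major events are stroke, pump thrombosis, severe bleeding and peripheral arterial thromboembolism. The primary comparison sets 30 apixaban patients against 15 controls.

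The SAP repeats the endpoint, which "will be evaluated as primary endpoint as proportion of success calculated between the apixaban and the warfarin arms". It gives no threshold, test or margin.

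Protocol section 2.2 reads: "The secondary endpoints include an evaluation of the following adverse events per INTERMACS definitions (version 5.0) throughout the study period". The 13 items that follow, repeated in the SAP, are all adverse events or death. Protocol section 5.3 adds prevalence and incidence of adverse events and rehospitalizations, and the SAP adds Kaplan-Meier analysis.

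Regimen data are collected. Section 5.2.6 states: "Any changes to the designated antithrombotic regimen based on randomization algorithm will be documented". Table 1 in section 5.2 marks the antithrombotic regimen at baseline, weekly, at ambulatory visits and at events. Appendix III has fields for date, medication and dosage, and for any change at an event. Section 5.2.8 records transplant, death, explant and withdrawal. None of these fields is tied to an endpoint or an analysis.

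**The concern.** One part of asking whether apixaban is feasible in these patients is whether they can be kept on it. An endpoint built only from deaths and major events does not see that part. A patient who goes back to a Vitamin K antagonist early and is event-free at day 90 contributes the same result as one who took apixaban throughout.

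This route off the drug is foreseeable from the Protocol. Under section 3.3.2 a committee reviews suspected as well as confirmed events and decides whether the patient can continue in the assigned arm. A suspected event that is not confirmed could end assigned treatment without a primary failure. Transient ischemic attack, hemolysis and liver or kidney dysfunction are tracked in section 2.2 but are not among the major events in section 2.1.

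Section 1 says that feasibility in HeartMate 3 patients has not been systematically studied before, so readers may lean on this trial's answer. Without a planned persistence figure, they also cannot tell how much of the apixaban group's event-free record was obtained on apixaban.

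**Working it through.** The plan states no feasibility figure, so there is none to reproduce. The group sizes agree: 3 × 15 = 45 and 30 + 15 = 45.

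**Step 1. Does any planned quantity depend on regimen status?**
- Primary endpoint (Protocol 2.1, SAP): death and four types of major event. No.
- Secondary endpoints (Protocol 2.2, SAP): 13 adverse events or death. No.
- Other analyses (Protocol 5.3, SAP): adverse event and rehospitalization rates, Kaplan-Meier. No.
- Regimen fields (Table 1, 5.2.6, Appendix III): collected, with no analysis planned.

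**Step 2. Inputs for an illustration.** The apixaban group is n = 30 (Protocol 2.1). The number stopping apixaban without a major event, d, and the number with a major event or death, h, are assumed, because the documents give no rate for either. Those who stop are taken to be different patients from those with events.

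**Step 3. Formulas.**
- Endpoint as written, all randomised patients counted: (30 − h)/30.
- Event-free and still on apixaban: (30 − h − d)/30.
- Those who stop left out of numerator and denominator: (30 − h − d)/(30 − d).
- Exact (Clopper-Pearson) 95% limits for x of n: lower = 0.025 quantile of Beta(x, n − x + 1); upper = 0.975 quantile of Beta(x + 1, n − x). For 30/30 the lower limit is 0.025^(1/30) = 0.884 and the upper is 1.

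**Step 4. Results.**

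| h | d | As written | Event-free and on apixaban | Those who stop left out |
|---|---|---|---|---|
| 0 | 0 | 30/30 = 100% (88.4 to 100) | 30/30 = 100% (88.4 to 100) | 30/30 = 100% |
| 0 | 5 | 30/30 = 100% (88.4 to 100) | 25/30 = 83.3% (65.3 to 94.4) | 25/25 = 100% |
| 0 | 15 | 30/30 = 100% (88.4 to 100) | 15/30 = 50.0% (31.3 to 68.7) | 15/15 = 100% |
| 2 | 10 | 28/30 = 93.3% (77.9 to 99.2) | 18/30 = 60.0% (40.6 to 77.3) | 18/20 = 90.0% |

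**Step 5. Reading.** The first proportion does not contain d, so it cannot move with stopping. Leaving out those who stop does not help. With no events the result is 100% for every d in the table. With two events it moves from 93.3% to 90.0% only because the same two events stand over 20 patients instead of 30.

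**The case against.** The strongest reply is that the documents never define feasibility as staying on the drug. Sections 1 and 2.1 can be read clinically: whether these patients can be supported on apixaban without hemocompatibility events. On that reading the endpoint fits, and counting every randomised patient regardless of later treatment is a defensible choice for safety. That choice should stay. But the clinical reading does not make persistence irrelevant to a claim that apixaban use is feasible, and the plan gives no other measure of it.

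Three stronger conclusions are tempting, and the documents do not support them.
- A reader might infer that the trial cannot return a negative answer on feasibility. It can: more strokes, pump thromboses, severe bleeds or deaths on apixaban than on control would be one.
- A reader might infer that a rule would declare apixaban feasible, or that the plan expressly scores switchers as successes. There is no such rule, and the SAP leaves the overall judgement of clinical safety to the oversight committee. No analysis set or rule for switching is stated. Counting switchers as successes follows from the endpoint's wording and from the 30 against 15 comparison, and remains an inference.
- A reader might infer that switches will be hidden. They are recorded, and nothing prevents reporting them. What is missing is the commitment to do so.

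It is also fair to say that the size is unknown. These are stable outpatients followed for 90 days for the primary endpoint, investigator-judged non-compliance is an exclusion, and confirmed major events already count as failures. Few may stop. That limits the expected effect, but it does not supply the missing measure.

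**Conclusion.** The point holds in a limited form. The endpoint assigned to feasibility responds to major events and death but not to patients leaving apixaban, and no other planned analysis fills the gap. In the assumed event-free case, 100% as written stands beside anything from 100% down to 50% event-free and on the drug, as the number stopping goes from 0 to 15 of 30. These counts show the insensitivity; they do not forecast how many will stop. The as-written figures assume that all 30 are counted, but excluding those who stop would not reveal the problem either.

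This is an inexpensive improvement to the plan. It is not a fault in the primary endpoint as a measure of safety.

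**What to change.** 1. Keep the primary endpoint for safety, and state that it is counted in all randomised patients.
2. Add to Protocol section 2.2 and to the SAP a secondary feasibility endpoint: the proportion of patients randomised to apixaban who are still on apixaban at day 90, with exact 95% CI, overall and by aspirin subgroup. Tabulate reasons for stopping, and show death, transplant and explant separately so that they are not read as failure to tolerate the drug.
3. Report aspirin changes and control-arm switches descriptively. A patient who changes only aspirin then does not count as having left apixaban.
4. Base the feasibility statement on this figure together with the primary endpoint.

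Keeping persistence as its own proportion, and not folding it into an event-free composite, avoids merging safety and feasibility again. Two definitions need a sentence each in the SAP: how a temporary interruption spanning day 90 is classified, and the day from which 90 is counted, since section 2.1 counts from enrollment and section 3.2 from transition.

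The cost is a few lines of text. Regimen status, dates and outcomes are already collected. Appendix III asks what was changed but lists no field for why, so one such field may be needed in the spreadsheet. The downside is one more reported figure, possibly less favourable than the primary.

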### 3.2 STUDY DURATION

Patients enrolled will be followed-up for 90 days post-transition to a designated antithrombotic regimen based on randomization. Provided the individual patients clinical course is uneventful regarding the primary endpoint, the patient's follow-up within the antithrombotic study protocol will be extended to the next pre-specified time point for analysis at 180 days. After the 180 days timepoint is reached, the patients will be given a chance to prolong the study until 1 year. All apixaban subsets will be treated according to their original study arm, the patients from the Vitamin K antagonist and aspirin group will be randomized in a 1:1 manner to apixaban with or without aspirin.

If the individual uneventful primary safety endpoint is established, the patient follow-up will be prolonged with next pre-specified time point for analysis at 1 year. If the second safety endpoint is reached, the patients could be followed for the duration of support with the HeartMate 3.

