### 3.3 STUDY DESIGN

### 3.3.1 Study design

Stable HM3 patients who have not suffered a Major hemocompatibility-related adverse event after index hospitalization discharge and are at least 3 months postimplant will be screened for participation in the study. Upon meeting the study criteria and patient informed consent, the individuals will be randomized to either continued therapy with a Vitamin K antagonist and aspirin or conversion to apixaban 5 mg twice a day in a 2:1 manner (dose targeted to renal function); the apixaban group will be stratified further by 1:1 randomization to continued use of 100 mg aspirin once daily or cessation. Thus, 45 patients are planned to be enrolled and randomized in 3 subgroups of 15 patients in each arm (see Appendix I). After 180 days follow-up is reached, the Vitamin K antagonist and aspirin arm will be transitioned to apixaban and randomized in a 1:1 manner to groups with or without aspirin.

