### 5.2 DATA COLLECTION & FOLLOW-UP ASSESSMENTS

The patient will be assessed at baseline. Lactate dehydrogenase (LDH) will be assessed once a week for 4 weeks, then once every 2 weeks for the next month and monthly thereafter; TTE ECHO follow–up will be performed at baseline, at 1 month and at 3 months, followed until study completion per site standard of care. A complete list of data fields to be collected is provided in Appendix II. A summary

of the data collection is provided in Table 1 below, and follow-up assessments are further described in the following sections.

	Baseline 	Once a week 	Once a month 	During regular ambulatory visits	At time of event
Consent Form	х				
Demographics & Medical History	х				
Enrollment form	х				
Laboratory Assessment (study site standard of care)	х		х	х	х
LDH Assessment	х	X 	X 	х	х
ECHO assessment	х		X 	Х	х
Anti-coagulation / anti-platelet regimen	х	Х		х	х
Adverse Events: thrombosis, other adverse events					х
Rehospitalizations / Reoperations					х
Outcome					Х

 Baseline is defined as the time point of the patient enrollment to the study.

 The follow-up assessments commence after the study enrollment.

 LDH assessment once a week for 4 weeks, then once every 2 weeks for the next month and monthly thereafter

 ECHO follow–up will be performed at baseline, at 1 month and at 3 months, followed by periodical 6-monthly examinations

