#### 5.2.4 Laboratory Assessments and Diagnostics

LDH assessment will be performed once a week for 4 weeks after the randomization, then once every 2 weeks for the next month and monthly thereafter; other regular laboratory assessments will include standard of care work-up, including measurements of kidney and liver function and hemostasis. Desirably, the same local authorized laboratory facility should be used by the patients to ensure consistency of a laboratory follow-up.

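### Does the 90-day primary endpoint lack a consistent day 0 across the protocol and SAP?

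*Protocol*

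**What the plan says.** Section 2.1 of the protocol sets the primary endpoint as "survival free of major HRAEs (hemocompatibility related adverse events) at 90 days post-enrollment" and compares 30 apixaban patients with 15 controls.

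Section 3.2, on study duration, says: "Patients enrolled will be followed-up for 90 days post-transition to a designated antithrombotic regimen based on randomization". It then allows extension to 180 days with the condition "Provided the individual patients clinical course is uneventful regarding the primary endpoint".

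Section 5.3 and the SAP give 90 days without saying from when. The SAP also announces a Kaplan-Meier analysis without a time zero.

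The notes to the assessment table in section 5.2 state "Baseline is defined as the time point of the patient enrollment to the study" and "The follow-up assessments commence after the study enrollment". Appendix III has one field for the enrollment date and another for the date on which study therapy began. Both are marked in the Baseline column. No field for a randomization date appears there.

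**The concern.** A primary result expressed as a proportion at a fixed day needs one day 0, set before analysis and identical in every arm. Read side by side, sections 2.1 and 3.2 seem to offer two, and the sections that might settle the matter are silent.

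The worry is sharper because the arms differ in what happens at the start. Apixaban patients convert, while controls stay on what they were taking. Section 3.3.1 uses the word again for a later event: "After 180 days follow-up is reached, the Vitamin K antagonist and aspirin arm will be transitioned to apixaban". If the clock ran from the switch in the apixaban arms and from enrollment in control, events between enrollment and the switch would drop out of the apixaban count only. In a trial of 45 patients, one such event would be visible in the result. An origin left open could also be chosen after the events are known.

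Other wording adds to the impression that enrollment, randomization and start of therapy are treated as interchangeable. For example, section 5.2.4 says "LDH assessment will be performed once a week for 4 weeks after the randomization", whereas Appendix IV starts the same LDH schedule from initiation of therapy.

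**Working it through.** The plan states no figure for this point that could be reproduced. The check is a comparison of the texts, followed by an illustration on assumed inputs.

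**1. Which text defines the endpoint?**

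| Place | Subject | Origin |
|---|---|---|
| Protocol 2.1 | Definition of primary endpoint | Enrollment |
| Protocol 3.2 | Length of follow-up | Transition to randomized regimen |
| Protocol 5.2, table notes | Baseline; start of assessments | Enrollment |
| Protocol 5.3 | Analysis | None given |
| SAP | Primary proportion; Kaplan-Meier | None given |

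Only 2.1 assigns an origin to the endpoint. Section 5.2 agrees with it, and 5.3 and the SAP do not contradict it. Section 3.2 says how long patients are followed and when they may continue.

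**2. Can both statements be followed at once?** Let the switch occur T days after enrollment, with T ≥ 0. Follow-up under 3.2 runs to day T + 90, and T + 90 ≥ 90. The endpoint in 2.1 is therefore always observed in full. The days before the switch are covered too, because assessments begin after enrollment.

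**3. Does the origin work for controls?** Enrollment exists for every patient, so counting from it requires no transition date in the control arm.

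**4. How large could a difference be?** The gap T and the event risk are not in the documents. Assume a constant hazard, a 90-day risk p of 5% to 20%, and 30 apixaban patients.

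- Hazard: h = −ln(1 − p)/90 per day.
- First event in the gap (counted from enrollment, missed from the switch): f = 1 − exp(−hT).
- First event in the T days after day 90 (the reverse): b = (1 − p) × f.

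Worked case, p = 20% and T = 7: h = 0.2231/90 = 0.00248; f = 0.0172; b = 0.8 × 0.0172 = 0.0138. Expected patients: 30f = 0.52 and 30b = 0.41.

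| Gap T | Expected in gap, of 30 (p = 5% / 10% / 20%) | Expected after day 90, of 30 (p = 5% / 10% / 20%) |
|---|---|---|
| 0 days | 0 / 0 / 0 | 0 / 0 / 0 |
| 1 day | 0.02 / 0.04 / 0.07 | 0.02 / 0.03 / 0.06 |
| 3 days | 0.05 / 0.11 / 0.22 | 0.05 / 0.09 / 0.18 |
| 7 days | 0.12 / 0.24 / 0.52 | 0.11 / 0.22 / 0.41 |

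The chance that at least one of 30 is classified differently is 1 − (1 − f − b)^30. It is 0 at T = 0. It is 10% to 33% at 3 days and 21% to 61% at 7 days across these risks.

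**5. Which way would it push the result?** The two movements oppose each other. Both windows last 90 days, so among patients event-free at the start of each window a constant hazard gives the same risk p, and the expected net change is zero. If patients with an event in the gap were instead kept and scored as successes, the net shift would be f − b = f × p. At the extreme of this range that is 0.0172 × 0.20 = 0.0034, about 0.3 points.

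**The case for a change.** The strongest reply is that section 3.2 is more than a statement of duration. Its extension rule refers to the primary endpoint, so endpoint status could be understood as judged at the end of the post-transition period. The SAP should have closed that door and did not. Appendix III keeps two separate date fields, so the dates can differ, and no available text requires therapy to start on the enrollment day. One sentence would remove the doubt.

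Part of this stands. The wording is not aligned, the gap is not bounded in the text, and the study flow chart that might show the timing is not available. But the extension rule is a condition for continuing. A patient's status at enrollment plus 90 days is already known when the post-transition 90 days end, so the rule can be applied without a second endpoint clock.

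The control-arm point is weaker than it looks. The phrase in 3.2 refers to enrolled patients and a regimen set by randomization, which can include continued vitamin K antagonist with aspirin. The 180-day switch in 3.3.1 is a different event. The LDH schedule concerns safety monitoring and does not set the endpoint clock.

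Randomization might be a cleaner origin than enrollment. A patient with a major event between consent and randomization would meet an exclusion in section 4.2 and might never be randomized. Those days would then be event-free in every arm alike, since no arm has yet been assigned. This favors neither side, and Appendix III lists no randomization date to replace the enrollment date.

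**Conclusion.** The concern does not call for a change. An analyst who follows section 2.1 has one explicit day 0 that exists for all three arms, matches the protocol's baseline, is already recorded, and lies wholly within the follow-up in section 3.2. A Kaplan-Meier curve for the same endpoint would naturally start there. The silence in section 5.3 and the SAP is a gap with an obvious filling.

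The effect is exactly zero if therapy starts on the enrollment day, as the Baseline column of Appendix III suggests but does not prove. With a one-day gap, at most 0.07 of 30 apixaban patients would be expected to have a first event before the switch. Longer gaps make a single 3.3-point reclassification more likely, but they show no bias. The expected net shift is zero, or about 0.3 points at 20% risk and a 7-day gap if patients with an event in the gap are scored as successes. These sizes rest on an assumed constant hazard, assumed risks of 5% to 20% and assumed gaps of 0 to 7 days. They matter only if an analyst departs from the definition in 2.1. Repeating that origin elsewhere would tidy the text without altering the primary analysis.
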